6.2 QUANTITATIVE ANALYSIS

We will compare differences in all outcomes, each continuous variable, using MANOVA. Multiple linear regression will be used to adjust for baseline covariates.

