1.1 SPECIFIC AIMS

1.1.1 Primary Aim

Aim 1: To determine whether lactulose therapy improves self-reported HRQOL as assessed using the Short Form-8 Health Survey (SF-8).

1a. Comparison of SF-8 scores from baseline to 28 days, between the intervention and control arm.

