1.1.3 Exploratory Adverse Event Aims

Aim 5: To determine if lactulose therapy increases the incidence of >5 self-reported bowel movements per day.

5a. Comparison of self-reported episodes of >5 daily bowel movements from baseline to 28 days between the intervention and control arm.

Aim 6: To determine if lactulose therapy reduces the number of self-reported falls.

6a. Comparison of self-reported number of falls from baseline to 28 days between the treatment and control arm.

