1.2 END POINTS

All patients will be followed until death, liver transplantation or final study visit at 28 days post – enrollment.

Primary Endpoint

1. Comparison of SF-8 at 28 days post-baseline, between the two groups.

Secondary Endpoints

1. Comparison of ANT, overall sleep quality, regular daily activity impairment, falls, and average number of daily bowel movements at 28 days, compared between the two groups.

[figure not shown]

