4.3.2 Adherence Assessment

During the 28-day intervention phase, all subjects will be contacted on Study Days 3, 6, 9, 14, 15, 21 and 28 via automated REDCap email or SMS text messages via Twilio service. Study Day 28 will only be collected via REDCap email or phone. These points of contact are to collect data about stool frequency and consistency among all subjects and therefore lactulose adherence in the treatment group. If the subject opts out of Twilio service, the subject can also receive these questions via REDCap automated email or a study coordinator will collect this data from the subject directly via phone or email. On Study Days 3, 6, 9, 14, 21 and 28 subjects will be asked the following questions:

1. "How many bowel movements did you have yesterday? Please respond with a whole number." *If 0-4 bowel movements are reported the subject will exit the survey. If >4, the subject will receive the following instructions:*

Since you had > 4 bowel movements yesterday, please reduce to **one** 20g dose of kristalose (1 packet) packet per day. Please call the study line at [contact] if you continue to have more than 4 bowel movements daily or with any questions or concerns.

On Study Day 15 subjects will be asked:

2. "Please reference the Bristol Stool Chart we provided to you to answer this question. How would you describe your stool looks today? Please respond with the applicable number, between 1-7. *All subjects exit survey after response.*

1. Separate hard lumps
2. Sausage-shaped but lumpy
3. Like a sausage but with cracks on its surface
4. Like a sausage or snake, smooth and soft
5. Soft blobs with clear cut edges
6. Fluffy pieces with ragged edges, a mushy stool
7. Watery, no solid pieces, entirely liquid

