6. STATISTICAL CONSIDERATIONS

6.1 SAMPLE SIZE AND ACCRUAL

While no studies of lactulose enrolling patients exclusively with deficits in quality of life, one high quality study of lactulose therapy have been performed for patients with cognitive dysfunction defined by psychometric testing. Lactulose was associated with a 6.81 95%CI (5.2-8.4) point or 65% relative improvement in health-related quality of life using the Sickness Impact Profile compared to control. Given this magnitude of effect, very few patients need to be enrolled. However, if we hypothesize an attenuated effect (30% improvement), seeking to enroll with a 1:1 randomization, assuming an alpha of 0.05, we will have 90% power to detect a difference among 42 subjects. We will therefore proceed with a study of 50 patients to allow for additional adjustment of baseline covariates and drop-outs.

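### Section 6.2 does not fix an identifiable test of SF-8, the only primary endpoint: a literal MANOVA pools it with bowel movements, and an outcome-by-outcome reading leaves the score and covariates open

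*Combined protocol and SAP*

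**What the plan says.** Section 1.1.1 makes SF-8 the sole primary aim: "Comparison of SF-8 scores from baseline to 28 days, between the intervention and control arm". Section 1.2 gives the sole primary endpoint as "Comparison of SF-8 at 28 days post-baseline, between the two groups". The secondary endpoints in Section 1.2 are "Comparison of ANT, overall sleep quality, regular daily activity impairment, falls, and average number of daily bowel movements at 28 days".

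The analysis plan in Section 6.2 is two sentences: "We will compare differences in all outcomes, each continuous variable, using MANOVA", and then "Multiple linear regression will be used to adjust for baseline covariates". Section 6.1 raises 42 subjects to 50 "to allow for additional adjustment of baseline covariates and drop-outs". That wording hints that the unadjusted comparison leads and adjustment is extra, but no section says so.

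On the score, Section 4.1.1 describes physical and mental summary measures and eight domains. It does not choose among them or define a total. On covariates, Section 4.2.2 stratifies randomization by WPAI activity impairment (≤7 versus >7), but Section 6.2 names neither that stratum nor baseline SF-8.

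**The concern.** The primary claim needs one test that answers one question: did SF-8 improve more on lactulose than without it? Section 6.2 can be read in two ways, and neither fixes that test.

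**Joint reading.** A MANOVA across outcomes asks whether the arms differ on any combination of them. Average daily bowel movements is among them, and the protocol itself treats stool frequency as a sign of drug exposure and of side effects. One adverse-event aim is "To determine if lactulose therapy increases the incidence of >5 self-reported bowel movements per day". Of the scheduled messages, Section 4.3.2 says "These points of contact are to collect data about stool frequency and consistency among all subjects and therefore lactulose adherence in the treatment group". These are three distinct measures: the questionnaire average (the Section 1.2 endpoint), episodes above five per day (Aim 5), and message-based counts with stool form (adherence). Only the first enters through Section 1.2, but all three show that a bowel effect is expected. A significant joint test would then not show a quality-of-life benefit, and a real SF-8 effect could be diluted by outcomes that do not move.

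**Outcome-by-outcome reading.** SF-8 is tested, but the reader cannot tell in advance which summary score or which covariates. That matters in a trial of about 50 patients with an untreated control arm, no placebo and a self-reported endpoint.

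**Working it through.** **The plan's own figure.** Section 6.1 gives 90% power with 42 subjects, alpha 0.05, 1:1. It states no SD, no SF-8 effect and no sidedness, so 42 cannot be derived from the inputs. Solving backwards, two-sided with 21 per arm:
- Normal approximation: d = (1.960 + 1.282) × √(2/21) = 1.00.
- Exact t-test: d = 1.025.

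This does not show that 42 is wrong. It gives d = 1.025 as the effect the plan implicitly relies on.

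**Joint test.** A two-group MANOVA is Hotelling's T². With p outcomes and N = 50 (25 per arm), it is compared with F(p, N − p − 1), with noncentrality λ = (n₁n₂/N) × δ′R⁻¹δ = 12.5 × δ′R⁻¹δ. Here δ is the vector of standardized shifts and R is the correlation matrix. Six outcomes are those in Section 1.2. The four-outcome version drops sleep (a four-category item) and falls (a count), in case the plan's reference to continuous variables excludes them. The documents give no shifts or correlations, so those below are assumptions.

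*Only bowel movements shift, uncorrelated outcomes, alpha 0.05:*

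| Shift (SD) | λ = 12.5 × shift² | Six outcomes | Four outcomes |
|---|---|---|---|
| 0.3 | 1.125 | 9% | 11% |
| 0.5 | 3.125 | 19% | 23% |
| 0.8 | 8.0 | 47% | 55% |
| 1.0 | 12.5 | 69% | 77% |

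These are rates of a significant joint test when SF-8 does not change at all.

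*Only SF-8 shifts, N = 50:*

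| d | Correlation | Six outcomes | Four outcomes | t-test on SF-8 |
|---|---|---|---|---|
| 1.025 | 0 | 71% | 80% | 94% |
| 0.8 | 0 | 47% | 55% | 79% |
| 1.025 | 0.5 among all except bowel movements | 93% | 94% | 94% |
| 0.8 | 0.5 among all except bowel movements | 72% | 75% | 79% |

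In the correlated six-outcome case, δ′R⁻¹δ is 1.667 × d², which is why most of the loss is recovered.

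**Replacement test.** An ANCOVA on baseline SF-8 with correlation r raises the effective effect to about d/√(1 − r²), with 50 − 4 = 46 degrees of freedom against 48 for the t-test. At d = 1.025 this is 1.074 for r = 0.3 and 1.435 for r = 0.7. Simulated power for r = 0.3 to 0.7, with a 30% severe stratum unrelated to SF-8, is 96–99.9% at d = 1.025 and 82–97% at d = 0.8. The t-test has 94% and 79%. Its simulated false-positive rate is 5%.

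**If both SF-8 summaries are kept.** An unadjusted t-test at alpha 0.025 and d = 1.025 has 83.5% power with 42 subjects and 90% with 50. The 90% at 42 subjects in Section 6.1 would no longer hold.

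**The case against.** **The plan does name methods.** This stands. MANOVA and linear regression are both named, and a regression of SF-8 on arm and baseline covariates is already the model family proposed here. A reader might infer that the plan contains no test at all, which goes too far. What is missing is the specification that identifies the SF-8 test.

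**The joint reading may not be meant.** This has force. Aims 1a to 6a each state a separate comparison, Section 1.2 isolates SF-8, Section 6.1 powers a quality-of-life difference only, and the phrase about each continuous variable fits separate tests. A reader might infer that the trial will declare success on a global p-value driven by stool frequency, but no section says that a global result decides Aim 1. If the MANOVA only gated a later SF-8 test at 5%, false SF-8 claims could not exceed 5%. A simulation with SF-8 null and bowel shifts of 0.5, 1.0 and 1.5 SD gave 2.2%, 4.5% and 4.8%. The plan states no such follow-up, however, and a joint test remains the ordinary meaning of the word it uses.

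**Inflated error is not shown.** A reader might infer a false-positive rate of about 9–19%. Simulation gives 8.7–9.5% for the better of Day 28 and change scores, and 16–19% for the best of six analyses across both summaries. Those figures require picking the most favourable result, and nothing suggests that this is intended. Nor are the aim and endpoint wordings clearly rival analyses: the baseline-to-28-days phrase recurs across the aims and may only mark the time window.

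**Conclusion.** The point holds as a gap in specification with a clearly better method at hand. It does not show that the trial will misstate its result. Section 6.2 does not fix an identifiable test of SF-8, and its literal reading is a test that bowel movements alone can make significant: 19% of the time at an assumed 0.5 SD shift and 69% at 1.0 SD (six uncorrelated outcomes, 50 analysed). The power penalty is less certain. It is 71% against 94% if SF-8 alone moves and outcomes are uncorrelated, and close to nil at d = 1.025 if the other outcomes correlate 0.5. On the outcome-by-outcome reading neither problem arises, but the SF-8 score and covariates remain open. All shifts and correlations are assumptions. Severity: should fix.

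**What to change.** In Section 6.2:

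1. Replace MANOVA as the primary test with an ANCOVA of Day 28 SF-8 on arm, the baseline value of the same SF-8 score and the WPAI randomization stratum (≤7 versus >7). Analyse by assigned arm, two-sided 0.05.
2. Name one SF-8 summary score in advance. If the sponsor keeps both, test them with Holm, state that success on one supports a claim for that summary only, and restate Section 6.1, since 42 subjects then give about 83.5% and not 90%.
3. Align Sections 1.1.1 and 1.2 to this form.
4. Analyse the other outcomes separately, keep bowel movements out of any efficacy test, and make MANOVA supportive at most.

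The cost is text edits and two degrees of freedom; both covariates are already collected. Under the assumptions above, the ANCOVA has at least the power of the t-test.

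Two neighbouring matters need reconciling but are not part of this point. Section 4.2.2 puts baseline procedures before randomization, as this ANCOVA should have it, while Sections 4.2.1 and 4.2.3 put the baseline assessments after it. The handling of SF-8 forms completed early (Sections 4.7, 4.8 and 5.3) also needs a rule of its own.

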4.2.2 Randomization

After informed consent and baseline procedures are completed, the study coordinator will randomize the subject via reandomize.net. Subjects will be randomized in approximately equal allocation to each arm 1:1 lactulose therapy or the control group. Randomization is stratified by subject self-reported activity impairment level. Activity impairment level is determined by the baseline WPAI regular daily activity impairment score collected as part of the final screening questions (Appendix F): mild/moderate is a score of ≤ 7 , severe is a score of > 7 . To ensure approximate balance within arms, the randomization will be implemented using a randomly permuted blocks design to ensure approximate balanced assignments within subject self-reported

activity impairment severity level. The sequence of assignments for each stratum will be prepared in advance by a biostatistician.

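### Randomization is stratified by screening WPAI, but Section 6.2 does not commit any between-arm comparison to the stratum; if the stratum is prognostic, the MANOVA is conservative and loses some power

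*Combined protocol and SAP*

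**What the plan says.** Section 4.2.2 sets the design: "Randomization is stratified by subject self-reported activity impairment level". The factor is the WPAI activity item from the final screening questions (Appendix F). Eligibility requires a score of at least 3, so the strata are 3 to 7 and, in the protocol's words, "severe is a score of > 7". Within strata, "the randomization will be implemented using a randomly permuted blocks design"; the block size is not given.

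Section 6.2 is two sentences long. The first is "We will compare differences in all outcomes, each continuous variable, using MANOVA". The second is "Multiple linear regression will be used to adjust for baseline covariates", with no list of covariates. Section 6.1 adds that the planned 50 leaves room for covariate adjustment and drop-outs.

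Section 6 does not mention the stratification factor, either to include or to exclude it. It also does not say whether the MANOVA or the regression is the primary analysis of SF-8.

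**The concern.** Stratified blocks keep the arms nearly equal on the stratum, so between-stratum variation is largely removed from the treatment difference. An analysis without a stratum term still counts that variation as residual noise. Its standard error is then larger than the real sampling variation of the estimate, its confidence interval is too wide, and its test runs below the nominal 5%. The precision gained by stratifying is not used.

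This matters only if the stratum predicts the outcome, and there is reason to expect that it might. The screening item asks how far cirrhosis limits everyday activity, and several SF-8 items (Appendix C) ask about limits on physical activity, daily work and social life. The link should be strongest for the day-28 WPAI outcome, which repeats the stratifying item (Appendix G).

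The screening score is also the safest covariate available. Appendix F is completed before consent, so the score cannot be affected by knowledge of the assigned arm. For the baseline SF-8 the documents conflict: Sections 4.2.1 and 4.2.3 place it after randomization, and Section 4.2.2 places randomization after baseline procedures.

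**Working it through.** **Inputs from the documents.** Two strata and permuted blocks (4.2.2); "seeking to enroll with a 1:1 randomization", "assuming an alpha of 0.05" and "we will have 90% power to detect a difference among 42 subjects" (6.1); planned size 50.

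**Assumptions, not in the documents.** Two-sided test; blocks of 4; 30% or 35% of subjects in the severe stratum; normal outcome with total SD 1; a single-outcome test in place of the full MANOVA; share of outcome variance explained by the stratum (R²) from 0 to 0.30.

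**1. The plan's own figure.** Section 6.1 gives no SD, so the 42 cannot be reproduced independently. Solved backwards with 21 per arm:

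d = (1.960 + 1.282) × √(2/21) = 3.242 × 0.3086 = 1.00 SD.

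The t distribution gives 1.03 SD; a one-sided test would give 0.90 SD. About 1 SD is therefore the effect implied by the plan.

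**2. Formulas.** With n per arm, the comparison without the stratum reports SE = √(2/n), while the true SE under balanced strata is about √(2/n) × √(1 − R²). So:

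- True size without the stratum = 2 × [1 − Φ(1.96/√(1 − R²))] = 3.9%, 2.8% and 1.9% at R² = 0.10, 0.20 and 0.30.
- Power without the stratum = Φ[(d − 1.96 × SE reported)/SE true].
- Power with the stratum = Φ[d/SE true − 1.96].

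Example with n = 25, R² = 0.20 and d = 1.00: SE reported = 0.283 and SE true = 0.253. Power without is Φ[(1.00 − 0.554)/0.253] = 96.1%; power with is Φ[3.953 − 1.96] = 97.7%. At d = 0.8 the same formulas give 83.4% and 88.5%.

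**3. Simulation at the implied effect** (N = 50, 1.03 SD, 30% severe, 6,000 trials per setting; SEs taken from the null runs):

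| R² | SE without stratum: reported / true | Type I error: without / with | Power: without / with |
|---|---|---|---|
| 0 | 0.281 / 0.283 | 4.9% / 4.9% | 94.7% / 94.6% |
| 0.05 | 0.282 / 0.271 | 4.0% / 4.6% | 95.1% / 95.6% |
| 0.10 | 0.281 / 0.273 | 4.2% / 5.1% | 95.3% / 96.2% |
| 0.20 | 0.282 / 0.256 | 3.4% / 5.5% | 96.1% / 97.7% |
| 0.30 | 0.282 / 0.238 | 1.8% / 4.6% | 97.4% / 99.2% |

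The simulation error on a 5% rate is √(0.05 × 0.95/6000) = 0.3 points. The reported SE is too wide by about 10% at R² = 0.20 (0.282/0.256) and 18% at 0.30 (0.282/0.238). The power loss is 0 to 2 points. If only 42 subjects are analyzed, power is 90.4% against 92.2%, 91.3% against 95.0%, and 93.0% against 97.1% at R² = 0.10, 0.20 and 0.30, a loss of about 2 to 4 points.

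**4. A smaller effect** (N = 50, assumed 0.8 SD, 35% severe, 8,000 trials per setting). At R² = 0.10, 0.20 and 0.30, power without the stratum is 81%, 81% and 83%; with it, 84%, 87% and 91%. The loss is 3, 6 and 8 points. Type I error is 4.0%, 3.2% and 2.2% without, against 4.9%, 5.1% and 4.8% with.

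**The case against.** **The regression sentence may already cover it.** Section 4.2.2 describes the stratifying score as a baseline score, and Section 6.1 allows for covariate adjustment. A reader might infer from the MANOVA sentence that the plan has chosen to ignore the strata in every analysis. The documents do not support that: the regression could include the stratum. What stands is that nothing commits the analyst to including it, and no primary model is named.

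**The range of R² is assumed.** If a normally distributed score is split at 35%, a two-level stratum explains about 0.60 × r² of the variance. R² of 10%, 20% and 30% then needs underlying correlations of about 0.41, 0.58 and 0.71 between screening WPAI and SF-8 four weeks later. The upper end is demanding, because SF-8 also covers pain, energy and emotional items. This stands.

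**The outcome may be a change score.** Aim 1a compares SF-8 from baseline to 28 days, while Section 1.2 compares it at 28 days. If WPAI relates to both SF-8 values, much of the stratum effect cancels in the change. Take assumed correlations of WPAI with baseline SF-8, WPAI with day-28 SF-8, and the two SF-8 values with each other. At 0.4, 0.3 and 0.6 the stratum explains 0.60 × 0.3² = 5% of day-28 SF-8, but 0.60 × (0.3 − 0.4)²/(2 × 0.4) = 0.8% of change. At 0.7, 0.5 and 0.7 the figures are 15% and 4%. Other pairings give other values, but the loss could well be small for change. This stands.

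**An effect of 0.8 SD is not in the plan.** Correct. The figures at the implied 1 SD should be read first. That 1 SD is itself only back-solved, and the effect behind the sample size comes from a different instrument, the Sickness Impact Profile, so a smaller true effect is a fair sensitivity case.

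**Conclusion.** The point holds in conditional form. The MANOVA comparison has no stratum term, and the regression does not commit to one. If the stratum is prognostic, a comparison that omits it has standard errors that are too wide and a type I error of about 4%, 3% and 2% at assumed R² of 10%, 20% and 30%. If it is not prognostic, nothing changes. At 50 subjects the power loss is about 0 to 2 points at the implied 1 SD and about 3 to 8 points at an assumed 0.8 SD over that R² range.

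A reader might go further and conclude that the trial certainly loses power, or that its result would be unsafe. Neither follows. The documents give no WPAI/SF-8 correlation from which a loss could be established, and the error is conservative, so there is no added false-positive risk. This is a low-cost gain in precision that should be taken, not a threat to validity. All sizes rest on the assumptions listed in the working, including a single-outcome test in place of the MANOVA.

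**What to change.** Add to Section 6.2, in words such as: *Every between-arm comparison, including the primary SF-8 model, includes the randomization stratum (screening WPAI 3–7 versus above 7) as a fixed effect. A sensitivity analysis replaces the two-level term with the continuous screening WPAI score.* State in the same place which model is primary for SF-8, so that the sentence has a definite target.

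The cost is one degree of freedom in about 50. At R² = 0 the simulated power is 94.6% with the term and 94.7% without it, so there is essentially no penalty if the stratum turns out not to be prognostic. No new data are needed: the score is required for eligibility and for stratification, so it is held for every randomized subject.

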7. DATA COLLECTION AND MANAGEMENT

7.1 RECORDS TO BE KEPT

All data will be entered into case report forms (CRFs) using a REDCap platform. These forms include enrollment, baseline, intervention and outcome assessments. All data recorded in REDCap is identified by a unique Study Identification Number (Subject ID). The subject must read, understand, and sign an IRB approved informed consent form (ICF). The Investigator will retain the original signed consent form in a secured location. Additionally, we will upload a copy of original signed ICF into the subject's Michigan Medicine electronic medical record. Separate documents will be de-identified and stored in the University Share Drive.

7.2 ROLE OF DATA MANAGEMENT

The primary study coordinator will be responsible for data management. The study portal will provide a highly structured repository to store and process study data from electronic case report forms (e-CRFs), as well as to protect its integrity and confidentiality. This tool will assist study staff by providing efficient protocol management and study retention and oversight. Access to the study portal will be granted by the Investigator or primary study coordinator with differential access rights based on role.

7.2.1 Data Collection Protocol

- For enrollment, study staff will access the REDCap study portal via the web, and provide screening information about the patient.
- Study-related data, as outlined in the intervention procedures above, will be entered online by research staff into the CRFs within the REDCap study portal.

